Specific Aim 1 is to determine whether patients with asymptomatic carotid stenosis will differ in cognitive function compared to age-matched individuals without carotid stenosis but with similar vascular risk factors. The primary hypothesis is that in patients with asymptomatic carotid stenosis ($\geq 50\%$ diameter-reducing) who survive stroke-free for 2 years; the change in overall and domain-specific cognitive function will be significantly different compared to those without stenosis. The primary analysis of impact will be the overall and domain-specific cognitive change score at 2 years, with the initial score at recruitment serving as the baseline.

Patient recruitment

Eligible patients are defined as having asymptomatic $\geq 50\%$ diameter reducing carotid stenosis. Asymptomatic status in patients will be confirmed by a history, physical examination, and numeric NIH Stroke Scale96 as defined in prior NIH carotid trials1-4. While asymptomatic patients with diameter stenosis $\geq 60\%$ benefit from revascularization2, that benefit is reduced when compared to symptomatic patients1, 4. Most centers including

ours, follow the common practice of operating on symptomatic patients with stenosis, but only consider revascularization for asymptomatic patients when the stenosis is >80%^{45, 46}. In this standard of care approach, asymptomatic patients with moderate carotid stenosis (50-80%) are treated medically and followed with annual screening studies to monitor for disease progression. Once a decision has been made that they do not require revascularization, these patients will be recruited to our proposed study. The decision as to whether a subject is appropriate to be followed with medical management alone will be made by the treating clinician in consultation with their patient. Participation in this study will not require any change in the standard clinical care that patients receive.

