Tromso study	7/7/2010 11:41 AM	7/7/2010 11:41 AM
CREST REVIEW	7/7/2010 11:41 AM	7/7/2010 11:41 AM
Endarectomy for symptomatic carotid artery stenosis	7/7/2010 11:40 AM	7/7/2010 11:40 AM

3 * Provide a list of 3 keywords or search terms (1 per line) relevant to your research that would help potential participants find your study using search engines:

Keyword 1: Carotid

Keyword 2: Cognition

Keyword 3: Plaque

ID: VIEW4E02805A7E400
Name: v2_Supporting Literature

View: v2_Study Procedures

Study Procedures

If you uploaded a separate research protocol document in the 'Research Protocol' page, cite the applicable section and page numbers from that document in the answer boxes below. (If this study is a collaborative UM/VA study please list each procedure that is being conducted and the locations where it is being conducted.)

1 * Describe all procedures being performed for research purposes only (these procedures would not be done if individuals were not in the study) and when they are performed, including procedures being performed to monitor subjects for safety or to minimize risks:

The schedule for major evaluation components is provided in Table II of the protocol page 32

The time required to obtain the information is provided in Table III of the protocol page 32.

To assess the stated endpoints, our study will establish for each patient, the baseline demographics, vascular risk factor profile, neurologic status (history, neurologic examination, NIHSS), cognitive function (cognitive function tests), plaque information (3D B-mode imaging), microembolic counts (TCD testing), inflammatory status (serum pro-inflammatory markers), perfusion status (cerebrovascular reactivity) and quality of life (SF36, Frenchay index). To assess change in status we will measure for each patient,

follow-up cognitive function, plaque information, microembolic counts, inflammatory status, perfusion status, and quality of life, at 1 and 2 years post-recruitment. The stenosis-free control subjects will undergo an ultrasound carotid assessment at baseline (to rule out stenosis), and assessments of cognitive function at baseline and at 1 and 2 years post-recruitment.

**With regards to the planned additional follow-up, participants will attend one session of approximately 2 hours duration.

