Specific Aim 1 of the study will assess whether in patients with asymptomatic carotid stenosis $\geq 50\%$ who survive stroke-free for 2 years, change in overall and domain-specific cognitive function will be significantly different compared to those without stenosis. We will confirm the group distribution of demographic variables.

Additional analyses will be performed after correction for the age, education and mood status of patients. This hypothesis will be examined with analysis of covariance comparing the composite change scores for patients versus non-stenosed control groups at the 2-year time point after adjustment for the baseline cognitive function score. Although we anticipate the level of missing data due to missed visits to be modest, these analyses will be conducted using the mixed modeling approaches of Laird and Ware.

Specific Aim 2 (a through d) is designed to identify potential mechanisms of cognitive change in patients with asymptomatic carotid stenosis. We hypothesize that carotid plaque architecture, plaque composition, microembolic counts, serum pro-inflammatory markers, and cerebral hypoperfusion could each mediate cognitive decline. Within this aim, there are 2 hypotheses for each mechanism:

A) At 2 years, the features listed above will independently predict a change in cognitive function. The statistical approach for this aim will be identical to that of the hypothesis in specific aim 1. Associations with cognitive

change scores and plaque area, volume, composition, microembolic counts, serum pro-inflammatory marker levels and cerebrovascular reactivity will be assessed using the mixed models of Laird and Ware106. Power to detect associations of cognitive decline with each of these features can be estimated using the same approaches as for the hypothesis in aim 1. We have used the most conservative approach of dichotomizing these continuous variables at their median value – the actual analysis will be performed using the variables as continuous measures where the power will be greater. Using this very conservative approach for power calculations, the same detectable differences in change score of 0.4 SD with 90% power, and of 0.3 SD with 80% power, are achievable.

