Participants will be administratively withdrawn if they fail to comply with study procedures. This includes, coming for their baseline visit. Failing to come for their follow up appointments, or refusing to participate in all study procedures.

2 * Describe procedures for orderly termination:
Subjects will be contacted by telephone 3 times. If they refuse to come in or do not respond, their participation will be terminated and a note entered in their medical record and resaearch binder.

3 * Describe procedures that will be followed when subjects withdraw from the research, including partial withdrawal from procedures with continued data collection:
Subjects will be notified either by phone or letter that they have been withdrawn from the research. All procedures will be stopped and no further data will be collected. All data already collected will be used for analysis.

ID: VIEW4E1B52531F800
Name: v2_Withdrawal of Participants

View: v2_Privacy of Participants

Privacy of Participants

If the study does not involve interaction with participants, answer "N/A" to the questions below.

1 * Describe how you will ensure the privacy of potential participants throughout the study (**privacy refers to persons and their interest in controlling access to themselves**):
All subjects will have privacy i.e the right to control access to themselves. Study interviews will be held by a member of the study team only.

2 * Describe the location where potential participants will receive research information and detail the specific actions the study team will take to ensure adequate privacy areas:
In a private setting. Consent will be obtained by the PI or his team in writing. The evaluation to sign consent form will be used to determine mental eligiblity of the consenting individual.

3 * Describe potential environmental stressors that may be associated with the research:
We do not identify any potential stressors with this research.

ID: VIEW4E1B525B87C00
Name: v2_Privacy of Participants

View: v2_Confidentiality of Data

Confidentiality of Data

1 * Will stored research data contain identifiers or be able to be linked to and identify individual participants (either directly or through a code/research ID)?
Yes

2 * Where will research data be kept (address electronic and paper data as applicable)? (If this is a VA study please list specific sites that data will be kept.)

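### The withdrawal rule ends all data collection and offers no cognitive-only follow-up, so some obtainable 2-year primary outcomes are never sought

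*Combined protocol and SAP*

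**What the plan says.** The rule is in Withdrawal of Participants.

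- Item 1 (withdrawal without agreement) gives a general ground: "Participants will be administratively withdrawn if they fail to comply with study procedures". It then gives particulars, which include: "Failing to come for their follow up appointments, or refusing to participate in all study procedures".
- Item 2 gives the steps: "Subjects will be contacted by telephone 3 times. If they refuse to come in or do not respond, their participation will be terminated".
- Item 3 asks what happens on withdrawal, including partial withdrawal with continued data collection. The answer describes no partial option: "All procedures will be stopped and no further data will be collected". Data in hand are kept: "All data already collected will be used for analysis".

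Three other places bear on it.

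- Justification, Objective, & Research Design, item 2, sets the primary outcome: "The primary analysis of impact will be the overall and domain-specific cognitive change score at 2 years".
- Sample Size and Data Analysis, item 2, plans Laird-Ware mixed models for Aim 1 and says of the expected loss: "Although we anticipate the level of missing data due to missed visits to be modest".
- Study Procedures, item 1, schedules six kinds of assessment for patients at 1 and 2 years: cognition, plaque imaging, microembolic counts, blood markers, perfusion and quality of life. For controls the list is shorter: "The stenosis-free control subjects will undergo an ultrasound carotid assessment at baseline (to rule out stenosis), and assessments of cognitive function at baseline", with cognition repeated at 1 and 2 years.

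**The concern.** The rule does not separate leaving a procedure, or missing a visit, from leaving the study. The primary outcome needs only a 50-minute cognitive battery. TCD, imaging and blood sampling serve Aim 2, so refusing them does not prevent the battery from being given. Someone who could not be brought in at year 1 might still attend a year later.

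The rule also works against the planned analysis. A mixed model copes well with a gap at year 1 followed by a score at year 2. It cannot recover a score that was never sought. A participant terminated after missing year 1 leaves only a baseline score, which says almost nothing about change.

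Two things are at stake: precision, and bias if the people lost differ in cognitive change and the two groups lose different shares. Missing appointments and not answering calls could plausibly accompany cognitive decline, and the patient schedule is the heavier one. Both are reasons to look, not findings.

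**Working it through.** **Which participants the rule affects**

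| Situation | Outcome under items 1 to 3 | Is a 2-year score forgone because of the rule? |
|---|---|---|
| Misses year 1, is reached and comes in | Stays in | No |
| Misses year 1, refuses to come in or does not answer three calls | Terminated | Yes, if the person would have come at year 2 |
| Attends and takes the battery, but declines TCD, imaging or blood | Depends on the reading of item 1 | Yes if refusing any one procedure counts; no if only refusing every procedure counts |
| Misses year 2 and does not respond | Terminated | Largely missing under any rule |

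The general ground in item 1 favours the broad reading of the third row. Item 2, which describes only people who do not come in, favours the narrow one. The text does not settle it.

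**The plan's power figure**

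Inputs: 142 per group, a difference of 0.4 SD and a t-test (Sample Size and Data Analysis, item 1); 90% power at 0.4 SD (item 2). Two-sided 5% is an assumption, since none is stated for Aim 1.

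A two-sample t-test with n = 142 per group and d = 0.4 has power 91.9%, consistent with the stated 90%. By the normal approximation, 90% power needs 132 per group. As 132/(1 − 0.07) = 142, the sample size has room for about 7% loss. The documents state no general dropout allowance; the remark that attrition is covered by the power analysis concerns stroke.

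**Precision, with assumed total loss equal in both groups**

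- 15% loss: 142 × 0.85 ≈ 121 per group, power 87.3%.
- 20% loss: 142 × 0.80 ≈ 114 per group, power 85.2%.

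**Bias in a comparison of completers**

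Let p and c be the shares lost among patients and controls, and g the excess decline in SD of those lost over those who stay, taken as equal in both groups. The completer mean overstates each group's true mean by its share lost times g, so

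bias in the group difference = (p − c) × g.

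All values below are assumptions.

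- p = 20%, c = 10%, g = 0.5 to 1.0: 0.10 × 0.5 = 0.05 SD to 0.10 × 1.0 = 0.10 SD, understating the difference.
- p = 10%, c = 20%, same g: the same size with the opposite sign.
- p = c: zero.

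**The part that the rule causes**

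Only people who would return if invited count. If 30% would return (assumption), with the same excess decline, the avoidable part of the first case is 0.30 × 0.05 = 0.015 SD to 0.30 × 0.10 = 0.03 SD. Against the 0.4 SD target that is 0.015/0.4 ≈ 4% to 0.03/0.4 ≈ 8%.

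**The case against.** The strongest reply is that the rule is milder than it looks. Termination follows three calls, and only for those who refuse to come in or do not respond; many of them would be missing at year 2 under any rule. Collected data stay in the analysis, and a mixed model uses a 1-year score from someone lost later. Even at 20% total loss, power is 85%. All of this stands. It limits the size of the problem, but it does not explain why a person terminated at year 1 should not be asked again at year 2.

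A reader might infer that one missed visit, or one declined blood draw, is enough for withdrawal. The first is contradicted by item 2. The second rests on one of two readings.

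A reader might also infer that the rule removes more patients than controls and so biases the comparison toward no difference. The documents do not support this. The rule is worded alike for both groups and no loss rates are given. The heavier schedule points one way. Against that, Study Procedures, item 2, ties patients' plaque imaging to their clinical visits to spare them extra trips, and describes no similar arrangement for controls. The direction is open.

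Nor can the 0.05 to 0.10 SD bias be read as the effect of the rule. It uses assumed rates, a completer formula rather than the planned model, and counts all loss as avoidable.

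**Conclusion.** The point holds in a limited form. As written, the rule forgoes 2-year cognitive scores that some participants would have given, and it fits poorly with an analysis chosen to tolerate missed visits. Whether declining a single procedure ends participation is unclear and needs to be stated.

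The effect on power is modest: about 92% at 0.4 SD with full follow-up, 87% at 15% total loss and 85% at 20%, with two-sided 5% and the loss rates assumed. Only part of that loss is due to the rule. Bias could go either way or be absent; it depends on the difference in loss between groups and on the excess decline of those lost, and the documents give neither. This is a cheap improvement to make, not a flaw that undermines the primary comparison.

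**What to change.** Amend Withdrawal of Participants, items 1 to 3:

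1. State that missing the 1-year visit, or declining imaging, TCD, reactivity testing or blood, does not end participation.
2. Allow cognitive-only follow-up. Invite everyone who has not withdrawn consent or met an existing protocol exit event to the 2-year battery, and repeat the three calls at that window.
3. Report withdrawals by group, with timing and reasons, so that the size and direction of any imbalance can be seen.

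The cost is a short amendment, some extra calls and scheduling. Study Procedures, item 3, already plans yearly cognitive testing beyond 2 years, so staff and process exist. VA-Specific Criteria, item 2.1, records that recruitment is closed. For participants whose 2-year window has passed, only the reporting by group still applies.

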1.2 If No, who is responsible for payment?

2 * Who is responsible for the uncovered research-related costs?

There will be no uncovered research-related costs

2.1 If Other, specify:

3 If the participant is responsible for any research-related costs, identify and estimate the dollar amount:

ID: VIEW4E1B5D9641800
Name: v2_Research Related Costs

View: v2_Compensation for Research-Related Injury

Compensation for Research-Related Injury

1 * Is this study under a master agreement that includes a provision requiring the sponsor to provide compensation to participants for research-related injury?

 Yes No

1.1 If Yes, please provide the date and title of the agreement and upload the portion of the contract language relevant to compensation for research-related injury:

Name	Created	Modified Date
------	---------	---------------

There are no items to display

1.2 If No (the study is not under a master agreement), is there proposed contract language concerning payment to participants for treatment in the event of a research-related injury?

 Yes No

1.2.1 If Yes, indicate the status of the contract review/approval with the ORD and upload the proposed language relevant to compensation for research-related injury:

Name	Created	Modified Date
------	---------	---------------

There are no items to display

ID: VIEW4E1B629EEC000
Name: v2_Payment for Research-Related Injury

View: v2_Payment to Participants

Payment to Participants

1 * Will participants receive payment (money, gift certificates, coupons, etc.) for their participation in this research?

 Yes NoID: VIEW4E1C52A5D7800
Name: v2_Payment to Participants

View: v2_Payment Detail

Payment Detail**You indicated that participants will receive payment (money, gift certificates, coupons, etc.) for their participation in this research.**

1 * Payment to participants will be for: (check all that apply)

Travel
Parking
Time and effort

1.1 If Other, specify:

2 * What is the total dollar value of the payments over the duration of the study? **Total payment(s) for participation in research of \$600 or more is required to be reported on an IRS Form 1099.**

30.00

3 * Describe the timing and distribution plan for the payment (schedule, means, etc.)?

** Subjects that participate in the additional follow-up testing will be compensated with a check in the amount of \$30.00 that will be mailed directly to the subject. They will also be provided with a parking voucher that covers the cost of parking at any UMMC garage.

4 * Method(s) of payment to be Used:
Check

4.1 If Other, specify:

ID: VIEW4E1C54A6ACC00
Name: v2_Payment Detail

View: v2_HIPAA

HIPAA (Health Insurance Portability and Accountability Act)

1 * HIPAA applies to the University of Maryland School of Medicine, the University of Maryland School of Dentistry and the VA. Are you affiliated with, or will be accessing data from, any of these places? Yes No

2 If Yes, will the study view, access, share, collect, use, or analyze health information that is individually identifiable under HIPAA? Yes No

ID: VIEW4E1B0A2114400
Name: v2_HIPAA

View: v2_Protected Health Information

Protected Health Information (PHI)

You indicated that HIPAA applies and the study will view, access, share, collect, use, or analyze health information that is individually identifiable.

1 * Which PHI elements will be used or disclosed in this study? (Check all that apply)
Name
Address (if more specific than Zip Code)
Telephone numbers
Social Security numbers

2 * Why is the PHI necessary for this research?
If SSNs are going to be used, describe the specific use and type of SSN to be used (real, scrambled, last 4 digits).
The patients will be identified through their vascular lab studies. The PHI indicated is necessary to screen potential subjects for eligibility and contact those subjects to determine their desire to participate. The last 4 of the patients SSN is required to identify the patients in the patient record system at the VA. At the University of Maryland, the unique medical record number (MRN) will be used. SSN will not be used.

3 * What is the source(s) of the PHI?
The PHI will be collected from the VA computerized patient record system (CPRS)

4 * Provide written assurance that Protected Health Information will not be reused. (Note: this refers to re-use on another study or for a purpose which has not been approved, not to the re-use of screening data during the current study).
Protected health information will be kept secure at all times and will not be reused or distributed to any outside parties.

5 * How will permission to allow the use/disclosure of the individual's protected health information (PHI) be obtained? (Choose all that apply):
Obtain written authorization (*upload authorization form at the end of the application under "Consent and HIPAA Authorization Forms"*)
Requesting waiver/alteration of authorization (includes waiver of authorization for recruitment only)

5.1 If you are using a limited data set (LDS), please attach the Data Use Agreement (DUA):

Name	Created	Modified Date
------	---------	---------------

There are no items to display

ID: VIEW4E1B0A24AA400
Name: v2_Protected Health Information

View: v2_Waiver/Alteration of Authorization

Waiver/Alteration of Authorization

You indicated that a waiver/alteration of authorization is requested.

1 * Provide rationale for how the research presents no more than minimal risk to the privacy of individuals:
Information collected is for recruitment purposes only. The study team has taken steps to ensure the security of all patient protected health information. All information will either be stored on encrypted computers or kept behind two locked doors at all times.

2 * Describe the plan to ensure the protection of PHI collected during this study from improper use and disclosure:
Patient information will be stored on VA encrypted computers that are behind the VA firewall and password protected. Any paper information will be stored under two locks at all times at the VA research office 6B133.

3 * Describe the plan to destroy the PHI collected during this study at the earliest opportunity consistent with the conduct of the research. If there is a need to retain PHI, provide a justification:
In accordance with RCS 10.1, VA data can't be destroyed.

4 * Why could the research not practically be done without access to and use of this PHI?
Eligible patient's are defined as having a 50-70% percent stenosis of their carotid artery as verified by duplex ultrasound. Access to the patient's duplex study is required to determine eligibility.

5 * Why could the research not practicably be done without the waiver or alteration?

Without a HIPPA waiver we would be unable to identify eligible patient's and contact them regarding participation in the above mentioned study.

6 * Will the subjects' PHI be disclosed to (or shared with) any individuals or entities outside of UM?

Yes No

6.1 If Yes, describe the individuals or entities outside of UM to whom PHI will be disclosed.

PHI will be utilized by the VA Maryland Health Care System.

ID: VIEW4E1B0A2896400
Name: v2_Waiver/Alteration of Authorization

View: v2_Informed Consent Process

Informed Consent Process

If the study does not involve interaction with participants or a waiver of consent is being requested , answer "N/A" to the questions below.

1 * Indicate the type(s) of consent that will be involved in this study: (check all that apply)

Request to Waive Consent/Parental Permission (Consent is not being obtained)
Written Consent Form

2 * Describe the Informed Consent process in detail:

After explaining the protocol to potentially eligible patients, they will be given the opportunity to consider entering into the study. If they decide to enroll in the study they will be asked to sign an informed consent form .
Evaluation to sign consent form will be utilized to evaluate the capacity for valid informed consent.
Inability to respond adequately to questions on the evaluation form will indicate that the potential subject is not a suitable candidate.
This is a minimal risk study.

3 * Confirm that the consent process will explain the following:

- The activities involve research.
- The procedures to be performed.
- That participation is voluntary.
- The name and contact information for the investigator.

Yes No

4 * Describe who will obtain Informed Consent:

The PI and his research team

5 * If obtaining consent from a legally authorized representative (LAR), describe how you will confirm that the individual is the LAR and can provide legally effective informed consent. (Answer "N/A" if not obtaining consent from LARs)

N/A

6 * Describe the setting for consent:

The protocol will be explained to potentially eligible subjects. If they make a decision to enroll in the study they will be asked to sign a consent form and the HIPAA Document.

7 * Describe the provisions for assessing participant understanding:

The evaluation to sign consent form will be used to assess mental eligibility for entry into the study.

8 * Describe the consideration for ongoing consent:

This is a two year follow up study. Ongoing consent may not be necessary.

ID: VIEW4E1C661D0AC00
Name: v2_Informed Consent Process

View: v2_Waiver/Alteration of Consent Process

Waiver or Alteration Consent Process

You indicated that a waiver/alteration of consent is requested.

1 * Explain why the research involves no more than minimal risks to the subjects:

This request for waiver of informed consent is for recruitment purposes only, as required by the VA for studies that also obtain a waiver of HIPAA authorization for recruitment purposes. We will view information to determine eligibility but no research procedures will be conducted until such time that the participant agrees to take part in the study and signs the informed consent document. The recruitment process involves no more than minimal risk to the individual.

2 * Explain why a waiver or alteration of the consent process would not adversely affect the rights and welfare of the subjects:

This waiver request is for recruitment purposes only as required by the VA. If it is determined that the individual would be eligible to take part in the study, they will be approached and given the opportunity to agree and sign the informed consent document or they can decline participation.

3 * Informed consent is always required unless there is reason to grant a waiver or alteration of the consent process. Explain why you cannot carry out the research unless you are granted a waiver or alteration of the consent process:

This waiver request is for recruitment purposes only as required by the VA. If it is determined that the individual would be eligible to take part in the study, they will be approached and given the opportunity to agree and sign the informed consent document or they can decline participation.

4 If the research involves using identifiable private information or identifiable biospecimens, please explain why the research could not practicably be carried out without using such information or biospecimens in an identifiable format.

5 In some cases there will be additional pertinent information during the study that should be given to the participating subjects. For those subjects who have not been given informed consent because there is a waiver or alteration of the consent process, explain how the subjects will receive this additional important information. If applicable, please explain why a subject would not receive additional pertinent information.
N/A. Individuals who would be eligible to take part in the study will be given the opportunity to agree and sign the informed consent document or to decline participation.

6 If you are requesting an alteration of the consent process please explain why this request is necessary for the conduct of the research study. Please identify specifically what is being altered or changed in the consent process.
N/A

ID: VIEW4E1C73B344800
Name: v2_Waiver/Alteration of Consent Process

View: v2_Consent Forms - Draft

Consent and HIPAA Authorization Forms - Draft

1 Upload all of your Consent Forms for approval. Use only Microsoft Word.

Name	Created	Modified Date
ACCOF patient ICF 11-4-10	11/4/2010 8:37 AM	11/4/2010 8:37 AM
ACCOF VAMHCS Consent Stenosis 12_31_2014.doc	1/23/2015 11:09 AM	1/23/2015 11:09 AM
VA Consent Form CONTROL 9-4-12.doc	9/21/2012 8:36 AM	9/21/2012 8:36 AM
ACCOF VAMHCS Consent Control 12_31_2014.doc	1/23/2015 11:09 AM	1/23/2015 11:09 AM
ACCOF UMMC Consent Form Stenosis_8_12_13.doc	8/12/2013 11:25 AM	8/12/2013 11:25 AM
ACCOF control ICF 11-4-10	11/4/2010 8:37 AM	11/4/2010 8:37 AM
ACCOF UMMC Consent Form Stenosis 12_31_2014.doc	1/23/2015 11:08 AM	1/23/2015 11:08 AM
ACCOF UMMC Consent Form Follow-Up 6-13-17.docx	6/13/2017 10:51 AM	6/13/2017 10:51 AM
ACCOF UMMC Consent Form Control 12_31_2014.docx	1/23/2015 11:08 AM	1/23/2015 11:08 AM
ACCOF UMMC Consent Form Follow-Up 6-23-17 Revised.docx	6/23/2017 3:35 PM	6/23/2017 3:35 PM
ACCOF - Carotid Stenosis group 5-5-11	5/5/2011 9:18 AM	5/5/2011 9:18 AM
ACCOF VAMHCS Consent Template Stenosis 4_15_13.doc	4/15/2013 9:26 AM	4/15/2013 9:26 AM
ACCOF UMMC Consent Form Stenosis_Approved.doc	4/8/2013 9:00 AM	5/13/2013 9:10 AM
VA Consent Form STENOSIS Group 9-4-12.doc	9/21/2012 8:36 AM	9/21/2012 8:36 AM
ACCOF UMMC Consent Form Control_8_12_13.docx	8/12/2013 11:26 AM	8/12/2013 11:26 AM
ACCOF VAMHCS Consent Template Control 4_15_13.doc	4/15/2013 9:25 AM	4/15/2013 9:26 AM
ACCOF UMMC Consent Form Control_Approved.docx	4/8/2013 9:00 AM	5/13/2013 9:10 AM
ACCOF - Control Group 5-5-11	5/5/2011 9:19 AM	5/5/2011 9:19 AM
ACCOF VAMHCS Consent Form Follow-up 6-23-17 Revised.docx	6/23/2017 3:35 PM	6/23/2017 3:35 PM
ACCOF VAMHCS Consent Template Control 8_12_13.doc	8/12/2013 11:26 AM	8/21/2013 10:13 AM
ACCOF VAMHCS Consent Template Stenosis 8_12_13.doc	8/12/2013 11:26 AM	8/12/2013 11:26 AM
ACCOF VAMHCS Consent Form Follow-up 6-13-17.docx	6/13/2017 10:54 AM	6/13/2017 10:54 AM

IMPORTANT NOTE: the above list of consent forms (if any) are DRAFT versions. Under no circumstances should copies of these be distributed to patients/study subjects. If/when this research submission is approved by the IRB, approved consent forms will be available for download and use from the "Documents" tab of the Submission's workspace (click Exit and then look for the Documents tab - approved submissions only)

1A Archived Consent Forms:

Name	Created	Modified Date
There are no items to display		

2 Upload any HIPAA authorization forms here:

ACCOF UMMC HIPAA_Approved.doc revised HIPAA doc Nov 2011	4/8/2013 8:53 AM 11/22/2011 3:19 PM	4/8/2013 8:53 AM 11/22/2011 3:19 PM
---	--	--

Please refer to HRPO's website for specific instructions for preparing informed consent documents and to access current templates:
<http://hrpo.umaryland.edu/researchers/consents.html>

ID: VIEW4E1C7712D3000
 Name: v2_Consent Forms - Draft

View: v2_Organization Review Requirements (other than IRB)

Organization Review Requirements (other than IRB)

Answer the following questions to determine additional organizational review requirements:

1 **Department/Division Review** - All research submissions are required to undergo department/division/institutional review prior to IRB review. The following entity is listed as the required department/division/institutional review:

Vascular Surgery

If this information is incorrect, please notify the HRPO office.

2 **RSC Review Criteria** - select 'Yes' if the answer is 'Yes' for any of the following questions. Review by the Radiation Safety Committee may be required.

* 2.1 Does the research involve the use of ionizing radiation?

Yes No

2.2 Does the research involve the sampling of radioactive human materials for subsequent use or analysis in a laboratory?

3 **IBC Review Criteria** - select 'Yes' if the answer is 'Yes' for any of the following questions. Review by the Institutional Biosafety Committee may be required.

* 3.1 Does the research involve human gene transfer?

Yes No

-OR-
 Does the research specifically apply to human studies in which induction or enhancement of an immune response to a vector-encoded microbial immunogen is the major goal, and such an immune response has been demonstrated in model systems, and the persistence of the vector-encoded immunogen is not expected? This type of research is often referred to as recombinant vaccine trials.

3.2 Does the research involve the exposure of human subjects to pathogenic microorganisms, or the exposure of research staff to human subjects or samples known or reasonably expected to carry infectious disease(s)?

3.3 Does the research involve the sampling of materials from persons with no known infectious disease and where the only risk to study staff is occupational exposure to bloodborne pathogens as defined by the OSHA Bloodborne Pathogen Standard?

4 **Cancer Center Criteria** - Answer the following to determine if review by the Cancer Center (Hematology-Oncology) may be required.

* Does the protocol involve in any way studies related to the prevention, treatment, diagnosis, or imaging of neoplastic diseases?

Yes No

5 **General Clinical Research Center Review Criteria** - the GCRC offers free and/or cost shared resources for patient-oriented research. Click Here for more information.

Answer the following to determine if review by the GCRC may be required.

* Will the General Clinical Research Center (GCRC) facility or resources be used to conduct this activity?

Yes No

6 **VA Review Criteria** - Answer the following questions to determine if review by the VAMHCS R&D Committee may be required.

* 6.1 - Will the research be conducted by VA Investigators including PIs, Co-PIs, and Site Investigators on VA time (serving on compensated, WOC, or IPA appointments)? Yes No

* 6.2 - Will the research utilize VA resources (e.g., equipment, funds, medical records, databases, tissues, etc.)? Yes No

* 6.3 - Will the research be conducted on VA property, including space leased to and used by VA? Yes No

PLEASE NOTE that the research may be funded by VA, by other sponsors, or may be unfunded.

ID: VIEW4E1AF91AB2400
Name: v2_Organization Review Requirements (other than IRB)

View: v2_Institutional Biosafety Committee Review Required

Institutional Biosafety Committee Review Required

1 **NOTE:** based on your answers to questions on a previous page (see below) review by the Institutional Biosafety Committee (IBC) is required. This will involve extra steps on your (study team) part. Clicking the Continue button will result in the system creating a blank IBC Submission form for you. You will be required to fill out and submit this IBC form before you will be able to submit the Protocol form. The IBC Submission workspace and form can be reached by clicking the appropriate button on the left hand side of the Protocol submission's workspace (web page) after exiting the Protocol form.

2 **Question** - answered on IBC RSC review requirements page:

3.1 Does the research involve human gene transfer? - OR - Does the research specifically apply to human studies in which induction or enhancement of an immune response to a vector-encoded microbial immunogen is the major goal, and such an immune response has been demonstrated in model systems, and the persistence of the vector-encoded immunogen is not expected? This type of research is often referred to as recombinant vaccine trials.

Yes

3.2 Does the research involve: a) the exposure of human subjects to pathogenic microorganisms, or b) the potential exposure of UMB research staff to infectious materials through the sampling or processing of materials from patients with known infectious disease or from environmental surfaces?

3.3 Does the research involve the sampling of materials from persons with no known infectious disease and where the only risk to study staff is occupational exposure to bloodborne pathogens as defined by the OSHA Bloodborne Pathogen Standard?

If the answer to this question is wrong, an IBC submission is not required, use the Jump To menu or your browser's <

3 * **Confirm** - you have read the above information and understand that in addition to the IRB Protocol form, you will fill out and submit the IBC Submission form :

Yes No

ID: VIEW4E1AF91ED4C00
Name: v2_Institutional Biosafety Committee Review Required

View: v2_Use of Non-Veterans

VA-Specific Criteria

1 * **What is the relevance of this research to the mission of VA and the Veteran population that it serves?**
Prevents morbidity from carotid disease in veterans

2 * **Describe who will be enrolled in this study:**
Veterans and Non-veterans will be enrolled in this study

